## 7.3 Evaluating Adverse Events

AEs will be evaluated by an investigator who is a qualified medical physician.

### 7.3.1 Determining AE Severity and Grade

AE severity and grade will be evaluated according to the NCI Common Terminology for Adverse Events (CTCAE), version 4.0. Any AE which changes CTCAE grade over the course of a given episode should be closed at the date the severity changed and a new AE recorded on the AE case report forms from that date at the new severity.

### 7.3.2 Determining AE Causality

The Investigator must endeavour to obtain sufficient information to assess the causality of the AE and must provide his/her opinion whether the event has any relationship to the administered study treatment / procedure. This may require instituting supplementary investigations of significant AEs based on their clinical judgement of the likely causative factors and/or include seeking a further opinion from a specialist in the field of the AE.

Causality is the relationship of an AE to the IMP and will be determined as follows:

Definite:	

• There is clear evidence to suggest a causal relationship.

• Starts within a time related to the IMP administration and

• No obvious alternative medical explanation.

Probable:	

• There is evidence to suggest a causal relationship

• Starts within a time related to the IMP administration and

• Cannot be reasonably explained by known characteristics of the patient's clinical state.

Possible:	

• A causal relationship between the IMP and the AE is at least a reasonable possibility.

• Starts within a time related to the IMP administration

• However, the influence of other factors may have contributed to the event (e.g. the patient's clinical condition, other concomitant treatments).

Unlikely:	

• There is little evidence to suggest there is a causal relationship.

• There is another reasonable explanation for the event (e.g. the patient's clinical condition, other concomitant treatment).

• The time association is such that the trial drug is not likely to have had an association with the observed effect.

Not related:	

• The AE is definitely not associated with the IMP administered.

### 7.4 Serious adverse events (SAEs)

An SAE is defined as any untoward medical occurrence or effect that at any dose that:

- Results in death;
- Is life-threatening or places the patient, in the view of the investigator, at immediate risk of death from the event as it occurred;
- Requires in-patient hospitalisation or prolongs existing in-patient hospitalisation
- Results in persistent or significant incapacity or disability;
- Is a new cancer
- Is a congenital anomaly or birth defect;
- Is associated with an overdose (whether accidental or intentional). Any AE associated with an overdose is considered a SAE.
- Is any other medically important event.

 This does not include an AE which hypothetically might have caused death if had it occurred in a more severe form.

 Hospitalisation is defined as an unexpected inpatient admission, regardless of length of stay, even if the hospitalisation is a precautionary measure for continued observation. It does not usually apply to scheduled admissions that were planned before study inclusion or visits to casualty (without admission).

 A medically important event may not result in death, not be life threatening, or not require hospitalisation but may be considered a SAE when, based upon appropriate medical judgment, the event that may jeopardise the patient and require medical or surgical intervention to prevent one of the outcomes listed above.

#### 7.4.1 Reporting SAEs

All SAEs regardless of causality, pregnancy or overdose that occur from the first dose until the 30 day safety follow-up or the initiation of a new anticancer therapy, whichever is earlier, must be reported on the SAE report form within 24 hours of the investigator / designee becoming aware of the event.

The SAE/ECI report form should be sent to  
Email : [[contact]](mailto:[contact])  
[contact]  
who will in turn notify MSD of the event.

The SAE form must be completed, assessed for causality and expectedness against the current version of the Investigator Brochure, then signed and dated by the Principal Investigator or an appropriately qualified designated individual identified on the delegation log. The report will then be reviewed by the Chief Investigator (or a nominated representative) to confirm relatedness and expectedness. The NCI-CTCAE version 4.0 must be used to grade each SAE, and the worst grade recorded. If new or amended information on a previously reported SAE becomes available, the Investigator should report this to the Sponsor (via RM-CTU) on a new SAE report form. The Sponsor (via RM-CTU) will in turn submit the updated report to MSD. Please refer to the SAE completion guidelines for further information.

Additionally, any SAE considered by an investigator who is a qualified physician to be related to the IMP or protocol-specified procedure that is brought to the attention of the investigator at any time outside of the time period specified in the previous paragraph also must be reported immediately to the Sponsor (via RM-CTU) who will inform MSD.

#### 7.4.2 Events exempt from being reported as SAEs

Events specified in this section do not require reporting as SAEs in this trial, unless hospitalisation is prolonged for any reason and then an SAE form must be completed. The events must still be recorded in the appropriate section of the CRF.

1. Elective admissions to hospital for procedures which were planned and documented in the medical records at the time of consent are not SAEs, and do not require SAE reporting.

2. Hospitalisation for administration of the IMP, or to facilitate study procedures such as pharmacokinetic sampling according to the trial protocol, is also exempt from being reported as an SAE.
3. Progressive disease and death due to disease are not considered SAEs, unless they fulfil the seriousness criteria, as listed in Section 7.5. All cases of progressive disease and death should be reported in the CRFs

#### **7.4.3 Determining SAE Causality and Expectedness**

Assessment of causality and expectedness for all SAEs will be made by the PI/designee and Chief Investigator or delegate against the SmPC (Reference Safety Information Appendices). If updated versions of the SmPC are released during the course of the trial then assessment of expectedness will be made against the current regulatory approved version. The Reference Safety Information (RSI) for assessing the expectedness of adverse events is contained in section 4.8 of the Summary of Product Characteristics (SmPC).

### **7.5 Events of Clinical Interest**

#### **7.5.1 Definitions of Evidence of Clinical Interest (ECI)**

Selected non-serious and SAEs can also be classified as Events of Clinical Interest (ECI) and must be reported as described in section 7.5.2.

Events of clinical interest for this trial include:

1. An overdose of pembrolizumab, as defined in Section 7.6 that is not associated with clinical symptoms or abnormal laboratory results.
2. A Drug induced liver injury (DILI) defined as elevated AST or ALT lab value that is greater than or equal to 3X the upper limit of normal

**AND / OR**

An elevated total bilirubin lab value that is greater than or equal to 2X the upper limit of normal

**AND / OR**

An alkaline phosphatase lab value that is greater or equal to 2X the upper limit of normal, as determined by way of protocol-specified laboratory testing or unscheduled laboratory testing.

3. Any AEs identified in the below Table 12 can be classified as immune-related events of clinical interest. A detailed narrative of overdose and liver toxicity ECIs should be reported as described in section 7.5.2

A separate guidance document has been provided entitled “Event of Clinical Interest Guidance Document.” This document provides guidance regarding identification, evaluation and management of ECIs and irAEs. Patients should be assessed for possible ECIs prior to each dose. Lab results should be evaluated and patients should be asked for signs and symptoms suggestive of an immune-related event. Patients who develop an ECI thought to be immune-related should have additional testing to rule out other etiologic causes. If lab results or symptoms indicate a possible immune-related ECI, then additional testing should be performed to rule out other etiologic causes. If no other cause is found, then it is assumed to be immune-related.

### **7.5.2 Reporting of ECIs**

Overdose and liver toxicity ECIs whether or not related to the pembrolizumab, occurring from the first dose until 30 days following the last treatment dose, or the initiation of a new anticancer therapy, whichever is earlier, must be recorded on the AE e-case report forms and reported using the SAE/ECI report form within 24 hours of the PI/designee becoming aware of the event to the Sponsor (via RM-CTU) as follows:

The SAE / ECI report form should be sent to  
Email: [[contact]](mailto:[contact])  
[contact]  
who will in turn notify MSD of the event.

**Table 12:** Immune related Aes considered ECIs

Pneumonitis - (classified as ECI if <math>\geq</math> Grade 2)		
Acute interstitial Pneumonitis	Interstitial Lung Disease	Pneumonitis
Colitis - (classified as ECI if <math>\geq</math> Grade 2 or any grade resulting in dose modification or use of systemic steroids to treat the AE)		
Intestinal Obstruction	Colitis	Colitis microscopic
Enterocolitis	Enterocolitishemorrhagic	Gastrointestinal perforation
Necrotising colitis	Diarrhoea	
Endocrine – (classified as ECI if <math>\geq</math> Grade 3 or <math>\geq</math> Grade 2 and resulting in dose modification or use of systemic steroids to treat the AE)		
Adrenal Insufficiency	Hyperthyroidism	Hypophysitis
Hypopituitarism	Hypothyroidism	Thyroid disorder
Thyroiditis	Hyperglycemia, if $\geq$ Grade 3 and associated with ketosis or metabolic acidosis (DKA)	
Type 1 diabetes mellitus (if new onset)		
Hematologic – (classified as ECI if <math>\geq</math> Grade 3 or any grade resulting in dose modification or use of systemic steroids to treat the AE)		
Autoimmune haemolytic anaemia	Aplastic anaemia	Thrombotic thrombocytopenic purpura
Idiopathic thrombocytopenia purpura	Disseminated intravascular coagulation	Haemolytic uraemic syndrome
Any grade 4 anaemia regardless of underlying mechanism		
Hepatic - (classified as ECI if <math>\geq</math> Grade 2 or any grade resulting in dose modification or use of systemic steroids to treat the AE)		
Hepatitis	Autoimmune hepatitis	Transaminase elevations (ALT and/or AST)
Infusion reactions - (classified as ECI for any grade)		
Allergic reaction	Anaphylaxis	Cytokine release syndrome
Serum sickness	Infusion reactions	Infusion-like reactions
Neurologic - (classified as ECI for any grade)		
Autoimmune neuropathy	Guillain-Barre syndrome	Demyelinating polyneuropathy
Myasthenic syndrome		
Ocular - (classified as ECI if <math>\geq</math> Grade 2 or any grade resulting in dose modification or use of systemic steroids to treat the AE)		
Uveitis	Iritis	
Renal - (classified as ECI for <math>\geq</math> Grade 2)		
Nephritis	Nephritis autoimmune	Renal Failure
Renal failure acute	Creatinine elevations - (report as ECI if $\geq$ Grade 3 or any grade resulting in dose modification or use of systemic steroids to treat the AE )	
Skin - (classified as ECI for any grade)		
Dermatitis exfoliate	Erythema multiforme	Stevens-Johnson Syndrome
Toxic epidermal necrolysis		
Skin - (classified as ECI for <math>\geq</math> Grade 3)		
Pruritus	Rash	Rash generalised
Rash maculo-papular	Any rash clinical significant in the physicians judgement.	
Other - (classified as ECI for any grade)		
Myocarditis	Pancreatitis	Percarditis
Any other grade 3 event which is considered immune-related by the physician.		

## 7.6 Definition of an Overdose for this Protocol and Reporting of Overdose

At present no specific information is available on the treatment of overdose of pembrolizumab. For purposes of this trial, an overdose will be defined as any dose exceeding the prescribed dose for pembrolizumab by 20%. In the event of overdose the patient should be observed closely for signs of toxicity. Appropriate supportive treatment should be provided if clinically indicated.

If an AE(s) is associated with (“results from”) the overdose of pembrolizumab, the AE(s) should be recorded on the AE CRF and reported as a SAE, even if no other seriousness criteria are met.

If an overdose is taken without any associated clinical symptoms or abnormal laboratory results, the overdose is again recorded as an AE on the CRF and reported as a non-serious ECI, using the terminology “accidental or intentional overdose without adverse effect.”

All reports of overdose either SAE or ECI must be reported within 24 hours of the PI or designee becoming aware of the event to the Sponsor (via RM-CTU) as follows:

The SAE / ECI report form should be sent to  
Email: [[contact]](mailto:[contact])  
[contact]  
who will in turn notify MSD of the event.

## 7.7 Reporting of Pregnancy and Lactation

Although pregnancy and lactation are not considered AEs, it is the responsibility of investigators or their designees to report any pregnancy or lactation in a patient (spontaneously reported to them), that occurs during the trial or within 120 days of completing the trial, or 30 days following cessation of treatment if the patient initiates new anticancer therapy, whichever is earlier. All patients who become pregnant must be followed to the completion/termination of the pregnancy. Pregnancy outcomes of spontaneous abortion, missed abortion, benign hydatidiform mole, blighted ovum, foetal death, intrauterine death, miscarriage and still birth must be reported as SAE (Important Medical Events). If the pregnancy continues to term, the outcome (health of infant) must also be reported with the parents' consent. Such events must be reported within 24 hours to the Sponsor (via RM-CTU) as follows:

The SAE / ECI report form should be sent to  
Email: [[contact]](mailto:[contact])  
[contact]  
who will in turn notify MSD of the event.

## 7.8 Definition of a Serious Adverse Reaction (SAR)

A SAR is defined as an SAE that is judged to be related to any dose of study drug administered to the patient.

## 7.9 Definition of Suspected, Unexpected, Serious, Adverse Reactions (SUSARs)

A SUSAR is a serious adverse reaction, the nature or severity of which is not consistent with the applicable product information (e.g. reference safety information appendices of investigator's brochure for an unauthorised investigational product or summary of product characteristics for an authorised product). For lung stereotactic radiotherapy, the anticipated side-effects are listed in Section 6.1.2. Hospitalisations due to these adverse events, where causality is ascribed to lung stereotactic radiotherapy, will be reported as an SAE, but not escalated to a SUSAR.

## 7.10 Reporting of SUSARs

All SUSARs must be reported using the SAE report form within 24 hours of the PI/designee becoming aware of the event to the Sponsor (via RM-CTU) as follows:

The SAE / ECI report form should be sent to  
Email: [[contact]](mailto:[contact])

[contact]

who will in turn notify MSD, relevant Independent Ethics Committee (IEC) / Institutional review, appropriate regulatory authorities and the participating Principal Investigators of the event.

The Sponsor (via RM-CTU) will in turn notify the MSD, relevant Independent Ethics Committee (IEC) / Institutional review, appropriate regulatory authorities and the participating Principal Investigators in accordance with regulatory requirements and within the timelines as defined below:

- For fatal and life-threatening SUSARs the Sponsor (via RM-CTU) should report at least the minimum information as soon as possible and in any case no later than seven days after being made aware of the case.
- SUSARs which are not fatal and not life-threatening are to be reported within 15 days

Follow up of patients who have experienced a SUSAR should continue until recovery is complete or the condition has stabilised.

## 7.11 Annual Reporting of Serious Adverse Events

The Development Safety Update Report (DSUR) will be submitted annually on the anniversary of regulatory approval for the trial. This report will be submitted to regulatory authorities and Independent Ethics Committees (IEC) in accordance with all applicable global laws and regulations. Copies will be forwarded to MSD and Investigators.

## 7.12 Urgent Safety Measures

The Sponsor or Investigator may take appropriate urgent safety measures (USMs) in order to protect the patient of a clinical trial against any immediate hazard to their health or safety. This includes procedures taken to protect patients from pandemics or infections that pose serious risk to human health.

USMs may be taken without prior notification from the competent authority. However the CI/delegate must notify the Medicines and Healthcare Products Regulations (MHRA) the Research Ethics Committee (REC) and the Sponsor (via RM-CTU) of the new events and the measures taken and the plan for further action within 3 days of the measure being implemented. Should the site initiate a USM, the Investigator must inform the Sponsor (via RM-CTU) immediately either by:

Email: [[contact]](mailto:[contact])  
[contact]  
[contact]

The notification must include:

- The date of the USM;
- Who took the decision; and
- Why action was taken.

The Sponsor (via RM-CTU) will notify the MHRA and the Main REC within three days of USM initiation. RM-CTU will distribute the response and any subsequent amendments to the trial site.

## 8 DATA ANALYSIS AND STATISTICAL CONSIDERATIONS

---

### 8.1 Statistical Analyses

The final analysis will be conducted after one of the following conditions is met.

- The trial is terminated early (for example, due to toxicity).
- All patients have had the opportunity for treatment and have completed their 'off-study' visit.

Once one of the conditions is met, a data cut-off date will be established. All patient visits occurring on or before this date will be analysed and summarised in the final clinical study report. Any data collected after this date will be summarised in a supplemental report.

All data will be analysed using the statistical software STATA version 13. Quantitative data will be presented as number of observations, means, standard deviations, minimum and maximum values. Categorical data will be presented as frequencies and proportions. When appropriate, data will be presented either with 95% confidence intervals or exact binomial confidence intervals. Baseline characteristics will be summarised for all enrolled patients. Patients who died or withdrew before treatment started or did not complete the required safety observations will be described and evaluated separately. Treatment administration will be described for all cycles. Dose administration, dose modifications or delays and the duration of therapy will be described.

#### 8.1.1 Primary Endpoint

For the primary endpoint of establishing the MTD and RP2D of lung SBRT that can be safely combined with pembrolizumab, the toxicity rate will be stated as the proportion of patients who have had a DLT calculated along with an exact binomial 95% confidence interval. All toxicities will be tabulated by type, grade and dose level.

#### 8.1.2 Secondary Endpoints

Acute and late toxicity data will be tabulated by type, grade and dose level with the number, proportions and frequencies of grades 1-4 and grade 3-4 grades reported. The duration of clinical benefit assessed by overall response rate (ORR) defined as complete response (CR) or partial response (PR) and disease control rate (DCR) defined as CR, PR or stable disease (SD) using RECIST v1.1 & irRC (Appendix 6 & 7) will be calculated as a proportion of total treated with a 95% confidence interval. Differential response rates, defined as mixed responses , where some sites of disease shows a response to treatment, while other sites of disease show disease progression, will be measured as (yes/no). This will be calculated as proportions in the squamous cell and non-squamous cell histological sub-type giving associated 95% confidence intervals. Any differences will be assessed using a Chi squared test for proportions on differential response rates between histological subtypes. **PD-L1 staining is referred to as tumour proportionate score, reported as a percentage**

from 0–100%. It is classed as weakly positive (1 – 49%); strongly positive if >50%; and negative if <1%. The effect of PD-L1 expression on response rates will be measured using the proportion of patients recorded to be weakly positive, strongly positive or negative and tested using a Chi Squared test for proportions on expression level between responders and non-responders. PFS will be measured from the start of radiotherapy until radiological or clinical evidence of progression or death and will be censored at date of last follow-up for surviving patients. OS will be measured from the start of radiotherapy until death and will be censored at date of last follow-up for surviving patients. Median PFS and OS will be calculated using Kaplan-Meier methods giving associated 95% confidence intervals, respectively. All patients from Part A and Part B will be used to analyse secondary endpoints.

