Recent data supports the use of PD-1 inhibition in treatment-naïve advanced NSCLC patients. KEYNOTE-024 compared pembrolizumab against investigators choice of platinum-based doublet chemotherapy, enriched for PD-L1 positive patients (TPS  $\geq 50\%$ ). This shown a significant difference in median PFS favouring pembrolizumab (10.3 versus 6.0 months), and a significant difference in OS, again in favour of pembrolizumab (1-year OS of 80.2% versus 72.4%). The response rate was significantly higher in the pembrolizumab arm compared chemotherapy (44.8% versus 27.8%). The toxicity data did not reveal any new adverse events that were not already known about pembrolizumab, and again it was in support of pembrolizumab over platinum-based doublet chemotherapy (59). KEYNOTE-042 is of a similar design in an Asian population, but stratified patients into two PD-L1 positive groups: low expression (1–49%) and high expression ( $\geq 50\%$ ; NCT02220894), the results of which are still awaited.

Adverse events of grade 3–5 occurred in 13–16% of the patients receiving pembrolizumab, and 35% of the patients receiving docetaxel. Treatment discontinuation due to treatment-related adverse events was seen in 4–5% of patients receiving pembrolizumab compared with 10% receiving docetaxel. Treatment-related deaths occurred in three patients in the 2 mg/kg arm (2 with pneumonitis, and 1 with pneumonia), 3 patients in the 10 mg/kg arm (1 each with myocardial infarction, pneumonia, pneumonitis), and 5 patients on docetaxel (1 each with acute cardiac failure, dehydration, febrile neutropenia, interstitial lung disease, and respiratory tract infection). Immune-related adverse events occurred in ~20% of patients receiving pembrolizumab, with the most common being hyperthyroidism (4–6%), hypothyroidism (8%), and

pneumonitis (4-5%). The immune-related adverse events of grade 3-5 severity occurring in  $\geq 1\%$  of patients were pneumonitis (2%) and severe skin reactions (1-2%) (58).

These data have resulted in pembrolizumab being granted breakthrough therapy designation with the FDA for patients with NSCLC whose cancers have progressed on or after platinum-containing chemotherapy, as well as targeted agents in those with *EGFR* mutations and *ALK* gene rearrangements (60).

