### **2.2.2 Secondary Endpoints**

- To assess the rates of acute toxicity (defined as up to 12 weeks after the last fraction of stereotactic radiotherapy) using CTC AE v4.0.
- To assess the rates of late toxicity (defined as from 12 weeks after last fraction of lung SBRT until 28 days after the last dose of pembrolizumab) using CTCAE version 4.0.
- To calculate the ORR and DCR using RECIST v1.1 & irRC.
- To calculate the ORR and DCR in squamous versus non-squamous histological subtype using RECIST v1.1 & irRC.
- To assess the frequency of PD-1/PD-L1 expression distribution in responders and non-responders.
- To measure the PFS and OS at 6 and 12 months.

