### **3.4 Follow-Up after stopping Pembrolizumab**

#### **3.4.1 30 Day Safety Follow-Up Visit**

All patients will be required to attend a safety follow-up visit 30 days after the last dose of pembrolizumab or before the initiation of a new anti-cancer treatment, whichever comes first. All adverse events (AEs) and serious adverse events (SAEs) that occur prior to the safety follow-up visit should be reported as described in section 7. After the safety follow-up any unresolved AEs at the patient's last visit should be followed up for as long as medically indicated, but without further recording in the CRF.

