## 7.2 Assessing and Recording Adverse Events

All AEs will be recorded from the time of the first dose until the safety follow-up in the CRF. They will be followed up according to local practice until the event has stabilised or resolved, or the follow-up visit has taken place, whichever is the sooner. SAEs will also be recorded throughout the study. The reporting timeframe for AEs meeting any serious criteria is described in section 7.4.1.

Follow-up of AEs with a causality of possible, probable or highly probable will continue until the events resolve, stabilise or the patient completes the trial. Any unresolved AEs at the patient's last visit should be followed up for as long as medically indicated, but without further recording in the CRF.

If an Investigator learns of any AE that he/she consider serious, including death, at any time after a patient has completed the study and he/she considers there is a reasonable possibility that the event is related to pembrolizumab, the Investigator should notify the RM-CTU. Late toxicities will be recorded and reported as with other AEs.

The following details will be collected in the CRF for each AE:

- AE description / diagnosis
- Date of onset and date of resolution
- NCI-CTCAE grade maximum intensity
- Seriousness
- Investigator causality rating against the study medication (yes or no)
- Expectedness
- Action taken with regard to study medication
- Outcome

For the pre-registration period AEs will not be collected in patients that have not undergone any protocol-specified procedure or intervention. If the patient requires a blood draw, fresh tumour biopsy etc. for the study then the patient will be required to consent to the main study and AEs will be captured as described above.

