## **8.2 Sample Size**

During the dose escalation phase a standard 3+3 design will be used to recruit patients into two lung SBRT dose cohorts, firstly dose level 1 and then dose level 2, and both given the same pembrolizumab fixed dose level. Each cohort will require a minimum of 3 and a maximum of 6 patients. This means that there will be a minimum of 6 and maximum of 12 patients required for dose escalation. There will then be an additional 12 patients in the expansion phase. This number has been arbitrarily chosen to get a better appreciation for the toxicity profile of the dose/treatment that maybe taken forward in a phase II study.

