### **5. Grades**

Grade refers to the severity of the AE. The CTCAE displays Grades 1 through 5 with unique clinical descriptions of severity for each AE based on this general guideline:

Grade 1 Mild; asymptomatic or mild symptoms; clinical or diagnostic observations only; intervention not indicated.

Grade 2 Moderate; minimal, local or non-invasive intervention indicated; limiting age-appropriate instrumental ADL\*.

Grade 3 Severe or medically significant but not immediately life-threatening; hospitalization or prolongation of hospitalization indicated; disabling; limiting self-care ADL\*\*.

Grade 4 Life-threatening consequences; urgent intervention indicated.

Grade 5 Death related to AE.

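### The acute and late toxicity bands stop at grade 4, and the late window is empty for patients whose last pembrolizumab dose is on or before day 75, with no at-risk denominator given

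*Combined protocol and SAP*

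**What the plan says.** Section 8.1.2 tabulates acute and late toxicity by type, grade and dose level, "with the number, proportions and frequencies of grades 1-4 and grade 3-4 grades reported". Appendix 4 gives the grading scale, whose top category is "Grade 5 Death related to AE".

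The Trial Summary and Section 2.2.2 both define late toxicity; in 2.2.2 it is "defined as from 12 weeks after last fraction of lung SBRT until 28 days after the last dose of pembrolizumab". Acute toxicity covers the time up to 12 weeks after the last fraction.

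Section 8.1.2 closes with "All patients from Part A and Part B will be used to analyse secondary endpoints". It gives a denominator for response and disease control (those treated) but none for toxicity. Section 8.1 adds that patients who fell short of the safety observations asked of them will be described separately. It does not say which observations are meant or connect them to the late window.

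On data collection, Section 7.2 states "All AEs will be recorded from the time of the first dose until the safety follow-up in the CRF". After the 30-day safety visit, Section 3.4.1 has unresolved events followed "for as long as medically indicated, but without further recording in the CRF".

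**The concern.** Two features of the safety summary could make the combination look better tolerated than it is.

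First, a summary of severe toxicity that stops at grade 4 leaves out the most severe outcome. This can be foreseen here: Section 1.1.4.2 lists treatment-related deaths on pembrolizumab, including deaths from pneumonitis, and this trial adds lung irradiation. The same section reports "Adverse events of grade 3–5 occurred in 13–16% of the patients receiving pembrolizumab", so a grade 3-4 rate from this trial would not be like for like with that background figure.

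Second, the late window starts on a radiotherapy clock and ends on a drug clock. Patients who stop pembrolizumab early cannot have a late event by definition, whatever happens to the irradiated lung. If they are counted in the denominator, the rate falls for a reason unrelated to SBRT tolerability.

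Safety and tolerability are the primary objective, and Section 8.2 justifies the 12 expansion patients as being there "to get a better appreciation for the toxicity profile of the dose/treatment".

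**Working it through.** **Inputs.** Last fraction C1D19 = day 19; pembrolizumab every 21 days from day 1; C1D1 may move by 3 days against the SBRT days; maximum 24 patients (all Section 3.2). Late window from Section 2.2.2. First on-treatment CT at week 9 (Section 5.3.11.2). Median PFS 3.0, 3.7 and 3.9-4.0 months and median OS 10.4, 12.0 and 12.7 months on pembrolizumab (Section 1.1.4.2).

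**The plan's own figure.** Sections 3.2 and 8.1.4 equate 12 weeks after the last fraction with C6D1. 19 + 84 = day 103; C6D1 = 1 + 5 × 21 = day 106. The difference of 3 days is within the visit tolerance, so the figure reproduces.

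**Late window.** It opens on day 103 and closes at last dose + 28. It is empty when last dose ≤ 103 − 28 = day 75.

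| Last dose (on schedule) | Day | Window closes | Late days |
|---|---|---|---|
| C4D1 | 64 | 92 | none (11 days short) |
| C5D1 | 85 | 113 | 10 |
| C6D1 | 106 | 134 | 31 |
| C35D1 (about 24 months) | 715 | 743 | 640 |

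Moving C1D1 by 3 days shifts the cut-off to day 72 or 78; C4D1 still gives no window and C5D1 still gives one. A C4D1 delayed beyond day 75 would leave a short window. For a last dose at C4D1 the 30-day visit falls on day 94, so AE recording also ends before day 103.

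**How many patients (illustration only).** Assume exponential times, F(t) = 1 − exp(−ln 2 × t / (30.44 × median in months)). Take the share with a PFS event and subtract the deaths, since no window can observe patients who have died.

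- Progression first seen at the week-9 scan (day 64): PFS events by day 64 are 0.385 (3.0 months) to 0.305 (4.0 months). Deaths, at median OS 10.4 months, are 0.170 by day 85 and 0.202 by day 103. Upper end 0.385 − 0.170 = 0.215, or 5.2 of 24; lower end 0.305 − 0.202 = 0.103, or 2.5 of 24. About 3-5 patients.
- All stop at first progression, before C5D1 (day 85): PFS events by day 85 are 0.475 to 0.384. Less deaths by day 85, 0.475 − 0.170 ≈ 0.31 (7.3 of 24) to 0.384 − 0.170 ≈ 0.21 (5.1 of 24). About 5-7 patients.

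**Effect on the rate, two late events.** All treated: 2/24 = 8.3%. Removing 3-5 patients: 2/21 = 9.5% to 2/19 = 10.5%. Removing 5-7: 2/19 = 10.5% to 2/17 = 11.8%.

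**Grade 5.** The expansion dose level will hold 12 + 3 = 15 to 12 + 6 = 18 patients. One fatal event left out of the severe band is 1/18 = 5.6 to 1/15 = 6.7 percentage points. Across 24 patients, two with grade 3-4 and one with grade 5 would show as 2/24 = 8.3% in the planned band and 3/24 = 12.5% in a grade 3-5 band.

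**The case against.** **Grade 5 is not lost.** A reader might infer that fatal toxicities would go unreported. The documents do not support that: Sections 8.1.1 and 8.1.2 both tabulate by grade and dose level, a related fatal toxicity in the DLT period enters the DLT rate, and Section 7.4.1 requires related serious events to be reported even outside the usual period. No comparison with the 13-16% background figure is planned either. What stands is narrower: the two summary bands exclude grade 5.

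**The denominator is inferred.** A reader might take it as settled that patients without a window count in the late rate. The closing sentence of Section 8.1.2 could be only a statement that Parts A and B are pooled, and Section 8.1 may set some early leavers aside. Section 4.3 also replaces Part A patients who progress within about 3 months of radiotherapy. None of this resolves the point. Section 4.3 concerns DLT evaluability, and an early stopper who attends the 30-day visit has arguably done everything Section 8.1 asks. The plan is silent rather than clearly wrong.

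**All treated is a legitimate denominator.** The proportion of all treated patients with a late toxicity, with death as a competing event, is a valid quantity. A rate among those still observed at 12 weeks is a different, conditional one. This stands, and is the reason to report both.

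**A larger contrast is tempting.** Leaving out everyone with a PFS event by day 85 keeps about 13-15 of 24 patients, and two events become 13-15%. That also removes deaths, which no window could observe, and assumes that everyone stops at first progression. Sections 5.3.11.3 and 5.3.11.4 allow dosing until confirmation at least 4 weeks later, about day 92 after a day-64 scan, so a stable patient could be dosed at C5D1 and have a short window. The drug clock alone accounts for much less.

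**28 against 30 days.** Recording to day 30 and analysing to day 28 is not a contradiction, because the data cover the window. It is only untidy.

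**Conclusion.** The point holds as a reporting weakness of modest size. Two parts need no assumption: neither summary band can contain a grade 5 event, and the late window is empty for a last dose on or before day 75 and 10 days long for C5D1.

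Dilution of the late rate depends on reading Section 8.1.2 as counting all patients. Its size depends on exponential times and on medians from other pembrolizumab studies: about 3-5 of 24 patients if progression is first seen at the week-9 scan, up to 5-7 if all stop at first progression, and fewer if dosing continues to confirmation. With two late events, 8.3% becomes about 9.5-11.8%. Late observation would in any case range from nothing to about 640 days between patients.

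The endpoint is descriptive. Dose escalation and the RP2D depend on DLTs alone (Sections 3.2 and 3.2.1), so nothing here changes the dose decision.

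**What to change.** - In Section 8.1.2, report grades 1-5 and grades 3-5, worst grade per patient, by dose level.
- For late toxicity, give the rate among patients alive and under AE observation 12 weeks after the last fraction, beside the all-treated rate. By dose level, add the number at risk, the median late follow-up, and the number who left observation earlier, with deaths shown separately.
- State how the separate group in Section 8.1 relates to this denominator.
- Align the 28-day end of the window with the 30-day safety visit in the Trial Summary and Section 2.2.2.
- Recording SBRT toxicities at the existing 9-weekly follow-up visits may be considered. It should be optional and reported separately, because those visits cover only patients without progression and ascertainment would be uneven.

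The cost is wording in the Trial Summary and Sections 2.2.2, 8.1 and 8.1.2. No visits are added, and extra data entry arises only if the optional recording is taken up. The downside is a smaller late denominator with slightly higher reported rates. Late follow-up will still differ between patients, so its median needs to be shown.
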